**d. Study Endpoints:**

Albert Einstein Healthcare Network <hr/> Einstein	AEHN Protocol/Summary		
	NUMBER	DATE	PAGE
	HRP-204	11/1/2011	10 of 27

- i. Describe the primary and secondary study endpoints (*i.e. the outcome(s) that the study is designed to evaluate*): Overall, the study will examine motor functioning of the impaired arm as well as sensation in the limb as well as hemispatial neglect (participants with right hemisphere lesions only). The primary outcome measures will be the (1) upper extremity portion of the Fugl-Meyer test, a standard clinical measure of arm motor impairment, (2), Action Research Arm Test (ARAT), a valid and reliable measure of arm function in simulated ADLs, (3) the Rivermead Assessment of Somatosensory Performance (RASP), which tests proprioception, two-point discrimination, surface pressure touch, surface localization, and tactile extinction [121], and (4) in right hemisphere patients only, a virtual-reality assessment of navigation (VRLAT) developed by [name] [77], which is more sensitive to mild forms of hemispatial neglect than paper-and-pencil tests. Secondary outcome measures will be (1) the Stroke Impact Scale, a self-report measure of use of limb in activities of daily living (2) timed finger tapping, (3) maximum grip and pinch force, as assessed using a dynamometer, and (4) the Wolf Motor Function Test [78] to assess function limitations and allow comparison with the results of CIMT (used as a secondary measure because patients with lower Fugl-Meyer score will not be able to complete many items on this test).
- ii. Describe any primary or secondary safety endpoints (*e.g. any disease or symptom that would result in the withdrawal of that subject from the study*): N/A

#### e. Human Research Methods:

- i. Describe and explain the study design (*e.g. randomized, double-blind, placebo-controlled clinical trial or retrospective chart review*): randomized, placebo-controlled clinical trial
- ii. Describe all research activities involved in this protocol, including a study visit timeline if appropriate: C.5. PRE-TREATMENT ASSESSMENT: Should the patient meet the inclusion criteria, an additional battery of pre-treatment assessment tests will be completed as the first measure of the primary and secondary outcome measures. The primary outcome measures will be the (1) Fugl-Meyer test, described above, (2), Action Research Arm Test (ARAT), a valid and reliable measure of arm function in simulated ADLs, (3) the Rivermead Assessment of Somatosensory Performance (RASP), which tests proprioception, two-point discrimination, surface pressure touch, surface localization, and tactile extinction [121], and (4) in right hemisphere patients only, a virtual-reality assessment of navigation (VRLAT) developed by [name] [77], which is more sensitive to mild forms of hemispatial neglect than paper-and-pencil tests. Secondary outcome measures will be (1) Stroke Impact Scale [76], (2) timed finger tapping, (3) maximum grip and pinch force, as assessed using a dynamometer, and (4) the Wolf Motor Function Test [78] to assess function limitations and allow comparison with the results of CIMT (used as a secondary measure because patients with lower Fugl-Meyer score will not be able to complete many items on this test). Finally, the confirmatory behavior tests listed in Table 1 will be included in the pre-treatment assessment (see B.4 for details). We anticipate that the full pre-treatment screening can be completed in 2 90-minute sessions. De-identified data from both the inclusion screening and pre-treatment assessment will be discussed with the PI before brain scanning is undertaken (C.6) and the patient is assigned to a therapy group

Albert Einstein Healthcare Network <hr/> Einstein	AEHN Protocol/Summary		
	NUMBER	DATE	PAGE
	HRP-204	11/1/2011	11 of 27

(C.7.a) to ensure that the patient meets inclusion criteria and that no unusual combination of scores might suggest errors in data collection or scoring.

**C.6. LESION IDENTIFICATION:** Neuroimaging data will be analyzed to examine the relationship between treatment outcomes and lesion location & volume. Existing neuroimaging data may be used if the scan is an acceptable resolution. Scan data and processed (mapped) images may be obtained from the MRRI Cognition and Action or Language and Aphasia laboratories if available. Scan records from other facilities may be requested if necessary. However, for the majority of patients, a high-resolution MRI scan will be performed including a T1-weighted spoiled gradient-recalled-echo transverse images with 1-mm slice thickness, no gap, 1mm in-plane resolution with a 192 X 256 matrix. Images will be obtained on a 1.5T scanner at a single site (Hospital of the University of Pennsylvania). Based on past experience, 30% of the patients who consent to scanning will be unable or unwilling to undergo MRI scanning because of claustrophobia or medical contraindications (e.g., pacemaker, aneurysm clips, other metallic implants). These patients will have a CAT scan of the brain without contrast. CAT scans will be obtained on a 64-slice Siemens scanner at the University of Pennsylvania with 1.5 mm gap throughout. For analysis of brain-behavior relationships in brain lesion subjects, imaging data will be transformed to a common template ("Colin27" from MNI) using procedures outlined in [79]. Briefly, for MRI scans, lesions will be delineated in the subject's native space (that is, on the subject's MRI) by [name], an experienced neurologist and co-investigator. The structural scans and lesion maps will be registered to a common template using a symmetric diffeomorphic registration algorithm [80]. A single mapping from this intermediate template to the MNI-space "Colin27" volume will be used to complete the mapping from subject space to MNI space. For CAT scans, the Colin27 brain in MRICro will first be re-pitched to match the angle of acquisition of the subject's scan. The lesion contour identified in the patient's scan will then be manually drawn onto the template on a slice-by-slice basis by [name], taking into consideration the distance from the lesion margin and identifiable landmarks such as gyri, ventricles and subcortical structures. We have previously demonstrated excellent intra- and inter-rater reliability with this method [79]. [name] will be blind to the behavioral data when tracing lesions.

#### C.7. THERAPY REGIMEN

**a. Group assignment:** A research assistant (RA), who will not be involved in any assessments, will assign patients to the MT or placebo therapy (identical therapy with an opaque divider rather than a mirror) using stratified randomization based on the patient's Fugl-Meyer score. Before starting the trial an assignment order will be developed based on whether a patient's pre-treatment Fugl-Meyer score was low (between 10 and 30) or moderate (between 30 and 50). A previous MT RCT using a similarly chronic patient population and an identical placebo therapy showed little benefit of the placebo therapy. Thus, we must consider a balance between the scientific requirements of an appropriate control group and the ethical considerations of using patients' time to complete a therapy that is known to be ineffective. To balance these considerations, we will assign patients to the MT and placebo treatment groups in a 2:1 ratio, respectively. This inequality in sample size will only reduce statistical power by approximately 3% [81]. In addition, patients assigned to placebo treatment will be given the option of being crossed over to receive MT after the three month assessment. Patients will not be aware of which therapy is the placebo because both therapies will be described as studying the role of visual feedback rather than a test of "mirror therapy." Both treatments will include 2 daily 30 minute

Albert Einstein Healthcare Network <hr/> Einstein	AEHN Protocol/Summary		
	NUMBER	DATE	PAGE
	HRP-204	11/1/2011	12 of 27

therapy sessions, 5 days per week over a 4 week period.

b. Training therapies: Therapy instructions for both treatment groups will be presented using the same DVD shown using a portable DVD player. The 30 minute video will consist of 2 repetitions of a set of 15 movements including flexion and extension of the thumb, index, and middle fingers, opening and closing the hand, pinch grip with the thumb and index fingers, sequences of finger movements, wrist movement (pronation/supination, flexion/extension, radial/ulnar deviation), and flexion and extension at the elbow. Each trained movement will first be shown to the patient 3 times, after which the screen will go blank to allow the patient to focus on viewing their movements rather than the video monitor. A metronome sound will be presented on the video at 30 bpm and patients will be instructed to move in time with it. The metronome will run for 1 minute and 45 seconds followed by a 15 second rest break, after which the next movement will be presented. Instructions on the video will remind participants to make the same movement with both limbs "as well as possible" [19].

c. Compliance assurance: Several steps will insure that the treatment procedure is followed. First, at the start of each patient's therapy the device will be delivered to the patient's home by the RA, who will instruct the patient and caregiver on use of the system. The RA will lead the first session and then observe the second session. To further ensure compliance, and control for the timing of the mid-treatment assessments relative to the previous treatment session (see C.8), after every fifth therapy session (before day 6, 11, and 16) will be completed in the lab in the presence of the RA (and in a different room from the assessor) immediately prior to the mid-treatment assessment. Compliance outside of the RA's oversight will be assessed by including a simple, detachable, flash-memory video recorder on the mirror/divider apparatus. The video recorder will be selected for its ease of use (e.g., recording is done by pressing a single red button). Pilot testing with 7 patients indicated that patients had little trouble completing therapy outside of researcher supervision, and our use of video recording resulted in 100% compliance without any reports of difficulty using the video system. The RA will also deliver a pre-made therapy packet including a step-by-step checklist for each of the 20 therapy days, including a reminder to start the video recorder and questions to be completed before treatment (pain level) and after treatment (pain level, discomfort level, effort exerted during therapy, free-form question about any adverse effects). Before each mid-treatment assessment (see C.8), the RA will call and remind the patient and caregiver to bring the packet and recorder with them. The RA (who will know the therapy assignment) will download the video while the assessor completes the mid-treatment assessment. The RA will then view the video and confirm compliance with instructions regarding timing and production of movements. If non-compliance is discovered, the RA will discuss the issue with the patient. The RA will raise (without revealing the patient's group assignment) any compliance concerns with the PI.

C.8. MID-TREATMENT ASSESSMENTS: Three mid-treatment assessments will be performed, one immediately before every 5th day of therapy (before start of day 6, 11, and 16; see C.7.c), and will include only the primary outcome measures. The assessors will be unaware of group assignment, and before each session the assessor will remind patients to avoid mentioning any details of their therapy. The assessor will be given a questionnaire at the end of each assessment concerning the treatment to which they believe the patient has been assigned.

C.9. POST-TREATMENT ASSESSMENTS: The two post-treatment assessments (1 day and 3

Albert Einstein Healthcare Network  Einstein	AEHN Protocol/Summary		
	NUMBER	DATE	PAGE
	HRP-204	11/1/2011	13 of 27

months after final treatment session) will test both primary and secondary outcome measures. Procedures will be identical to mid-treatment assessments. To maximize retention at 3 months, the research assistant will make monthly calls to participants to maintain contact with the patient and be aware of any upcoming scheduling issues that might prevent timely follow-up.

- iii. Identify which tests/procedures are being administered solely for research purposes and which are being conducted as part of standard of care (i.e. procedures that would be done even if the participant were not involved in research): All tests are solely for research purposes. As a summary these tests are the screening tests (Fugl-Meyer, Western Aphasia Battery comprehension test, clinical hemianopia test, spatial action recognition test, Parson's test of hand laterality decisions, imagined grasping of objects) and assessment tests (Fugl-Meyer, Action Research Arm Task, Rivermead Assessment of Somatosensory Performance (RASP), virtual reality laterized attention task, Stroke Impact Scale, timed finger tapping, maximum grip and pinch force, Wolf motor function task) and brain scans (MRI or CT). Brain scanning (both MRIs and CTs) will be completed under a separate IRB protocol at the University of Pennsylvania with [name] as the site PI.
- iv. Describe steps taken to lessen the probability or magnitude of risks associated with tests/procedures being done for research purposes only (*e.g. only appropriately trained personnel involved in procedures, extra tests being done for safety purposes*): Risks to subjects from the behavioral tests are minimal. No adverse effects of mirror therapy have been reported. To protect against fatigue, subjects will be permitted to rest or discontinue testing at any time. Should subjects appear to be made anxious by the tasks, testing will be terminated. Subjects will be told that they are free to withdraw from the study at any time. A second potential risk comes from brain imaging. CVA subjects will undergo high resolution, anatomic MRI imaging using standard pulse sequences (e.g., T1-weighted, T-2 weighted, FLAIR and MPRAGE) or a CT scan of the brain. Brain scanning (both MRIs and CTs) will be completed under a separate IRB protocol at the University of Pennsylvania with [name] as the site PI. Neither gadolinium or iodine containing contrast will be administered. The major risk from MRI is that the strong magnetic field will dislodge a metallic object inside the subject's body (e.g., aneurysm clip) or interfere with an implanted device (e.g., cardiac pacemaker). Standard protocols have been developed at the University of Pennsylvania to ensure that subjects at risk do not undergo an MRI scan. This protocol includes an extensive checklist that is completed by the subject or family member; additionally, the MRI technician interviews patients prior to entering the MRI suite. A second potential concern comes from loose metallic objects in the MRI suite that can serve as missiles if they are drawn to a powerful magnet. Metallic objects that are not secured to the floor or wall are not permitted in the MRI suite. We note that these procedures have been employed in the clinical and research settings at the University of Pennsylvania for many years; no adverse effects from MRI scanning have been experienced to date. Subjects who are or think they might be pregnant will be excluded because the safety of MRI in pregnancy has not been established. The major risk from CT scan is a small dose of ionizing radiation. This procedure will be approved by the Penn IRB and subjects will be asked to sign a consent form in which the potential risks are discussed.

Albert Einstein Healthcare Network Einstein	AEHN Protocol/Summary		
	NUMBER	DATE	PAGE
	HRP-204	11/1/2011	14 of 27

v. Describe alternative treatments that are available to subjects if they choose not to participate in research: Participants will be notified in the consent form that they may choose traditional physical or occupational therapy if they do not wish to participate in the study.

vi. Describe the source records that will be used to collect data: MRRI Research Registry records, clinical MRI / CT scans; neuroimaging data from MMRI Labs [Perceptual-Motor Control Lab; the Cognition and Action Lab, and/or the Language and Aphasia Lab]

vii. Describe what data (variables) will be collected for this research: Times and accuracy at performing a number of movement tasks, sensory abilities, and general cognitive functioning; brain lesion information as determined by neuroimaging.

viii. Describe any plans to conduct audio or video recording of research participants during the conduct of the research. Specify whether recording is optional or not and how information on how recordings will be used and how long they will be retained is being shared with subject: All participants will be video-recorded during the behavioral experiments. Participants are informed of this during the informed consent process, and they will sign a separate permission to videotape document which will detail how long the videos will be retained.

#### **f. Specimen Management:**

i. Will any type of specimen (e.g. blood or tissue) be collected for this study?

Yes  
 No , skip to section on Data Management

ii. What information will be associated with the specimens collected for this study? [REDACTED]

iii. If specimens will be banked for future use, describe where and how the specimens will be stored:  
[REDACTED]

iv. Specify how long specimens will be stored locally: [REDACTED]

v. Specify who will have access to the specimens locally: [REDACTED]

vi. Will specimens be sent out or received:  No  Yes

- Who is responsible for receipt or transmission of the specimens? [REDACTED]
- How will specimens be transported? [REDACTED]
- Describe the procedures to release specimens, including: the process to request a release, approvals required for release, who can obtain specimens, and the data to be provided with specimens: [REDACTED]

#### **g. Data Management**

Albert Einstein Healthcare Network <hr/> Einstein	AEHN Protocol/Summary		
	NUMBER	DATE	PAGE
	HRP-204	11/1/2011	15 of 27

i. Describe steps that will be taken to secure the data (e.g. training, authorization of access, password protection, encryption, physical controls, certificates of confidentiality and separation of identifiers and data) during storage, use and transmission: All computerized data will be password and stored only on the network share drive.

ii. Describe the data analysis plan, including any statistical procedures and method for determining the sample size for the study: C.11. Testing Specific Aim 1 (benefit of home-based MT)

Tests for improvement in the primary and secondary outcome measures (see C.4) administered during the pre-treatment assessment and the two post-treatment assessments will be separately compared using ANCOVA analyses with post-treatment values as DVs, therapy type (MT, placebo) as the IV, and pre-treatment assessment score as the covariate [74]. Confirmation of MT's benefit will be tested in the main effect of therapy type.

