**1) Protocol Abstract** (*Briefly (in 250 words or less) describe the study in language understandable to a layperson. Include a brief description of the study purpose, target disease/condition if applicable, key eligibility criteria, and main study interventions*): Each year in the United States 550,000 people develop upper-extremity movement deficits after stroke (hemiparesis). The recent success of mirror therapy (MT) is notable because it is a simple treatment for hemiparesis, and may be feasible for home use. MT uses a standard mirror to create a compelling illusion in which movements of the unimpaired limb appear as if they are being made by the impaired limb. We propose to complete a randomized placebo-controlled clinical trial of home-based MT with a target enrollment of 100 chronic stroke patients. The therapy will consist of a standardized set of hand, wrist, and elbow movements completed in two daily 30-minute sessions, 5 times per week for 4 weeks. Patients assigned to the placebo treatment (identical therapy with an opaque divider rather than a mirror) will be crossed over to receive MT after a three month follow-up. The therapy will be performed by the participant within his/her home. This project will have two phases. The first phase, to be completed at Einstein, will include all of the behavioral testing. The second phase, to be completed at the University of Pennsylvania, will be limited to MRIs and CTs and will be completed under a separate IRB protocol at the University of Pennsylvania with [name] at the site PI.

**2) Project Objectives and Hypotheses:** The first goal of the study will be to determine whether a home-based form of MT is an effective treatment of hemiparesis. The second goal will be to determine the optimal dosing of MT by including weekly measures of improvement. The third goal will be to understand individual differences in the efficacy of mirror therapy. Previous MT studies have not reported, or lacked the power to test, why some patients benefit from MT and others do not, even though significant individual differences have been reported. Our use of a large sample of patients will allow us to assess predictors of therapeutic benefit.

Albert Einstein Healthcare Network <hr/> Einstein	AEHN Protocol/Summary		
	NUMBER	DATE	PAGE
	HRP-204	11/1/2011	2 of 27

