#### B.1. Understanding individual patient differences in treatment response

A critical, but often understudied, issue in rehabilitation is predicting individual patient differences in treatment response. As reviewed in section A.1, a wide range of therapies exist for the treatment of hemiparesis, and several recent RCTs comparing two active treatments have reported equivalent benefits at the group level [9, 30, 31]. It would be clinically valuable to understand the characteristics of patients who do and do not respond to each therapy given the magnitude of these individual differences. For example, in a recent RCT of MT for chronic stroke patients [20], improvement in the Brunnstrom scale outcome measure ranged from 0% to 33% (estimated from two standard deviation above and below the mean of 16.5% improvement). Information about predicted individual differences would be useful for clinicians when deciding the course of treatment most likely to benefit the patient.

We assert that individual differences in response to MT are predictable through an understanding of the mechanisms responsible for MT's therapeutic benefit. The assembled team composed of researchers trained in the basic science of sensorimotor control ([name]) and its application to stroke patients (Drs. [name], [name], and [name]) is uniquely positioned to address this issue. The project is innovative because it will test competing predictions regarding the mechanism of MT by utilizing individual differences in lesion location and the integrity of four sensorimotor processes that may underlie MT's benefit. As an overview, we will first discuss the four sensorimotor processes that may underlie the mechanisms of MT's benefit (B.2), and then proceed to a summary of the

Albert Einstein Healthcare Network <hr/> Einstein	AEHN Protocol/Summary		
	NUMBER	DATE	PAGE
	HRP-204	11/1/2011	4 of 27

neural substrates that subserve these processes (B.3). Following this will be a discussion of the behavioral tasks we will use as convergent validity tests of the neuroanatomic predictions (B.4). Finally, we will summarize all of these predictions in Table 1.

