**C.13. Testing Specific Aim 3 (predicting individual differences in therapeutic benefit)**

All tests of Specific Aim 3 will focus on data from the MT group only.

a. Testing predicted relationships between processes underlying MT and MT benefit using lesion location: We will examine the relationship between the change in primary and secondary outcome measures and lesion location using whole-brain voxel-based lesion-symptom mapping (VLSM) analyses [83]. VLSM measures whether a behavioral score systematically differs between participants with and without damage to each voxel under investigation. Tests of this difference use a t-statistic to describe the difference in means between the damaged-group and non-damaged-group while taking into account the variances within each group. The t-statistic is thus used as a convenient measure of group differences, without the intention of comparing it to the parametric t distribution. Instead, statistical significance will be determined by non-parametric permutation tests [84], in which the distribution used for inferential statistic calculations are created by sampling from the observed data rather than assuming an a priori distribution. Thresholds for significance will be calculated from the 95th percentile of this distribution, to ensure a family-wise false positive rate of 0.05 [84]. The total number of comparisons will also be reduced by only performing analyses on those voxels that are damaged in at least 10% of participants (to avoid undue influence of a small number of participants).

As in the previous measures, we will use an ANCOVA-like procedure to determine whether post-treatment scores (the DV) are affected by damage status to each individual voxel under consideration (the IV) after controlling for pre-treatment score and total lesion volume (covariates). Separate VLSM analyses will be done for each primary and secondary outcome

Albert Einstein Healthcare Network Einstein	AEHN Protocol/Summary		
	NUMBER	DATE	PAGE
	HRP-204	11/1/2011	16 of 27

measure. The voxels identified as being predictive of MT benefit using the VLSM analysis should be consistent with the a priori ROI predictions (Table 1). VLSM will also allow us to test whether voxels outside of these ROIs predict MT benefit.

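### The C.11 ANCOVA pools one residual variance across a 2:1 allocation: if response to MT makes that arm more variable, the Aim 1 test loses power and its intervals are too wide

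*Combined protocol and SAP*

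**What the plan says.** Section 6.g.ii, C.11, compares each primary and secondary outcome at the two post-treatment visits using "ANCOVA analyses with post-treatment values as DVs, therapy type (MT, placebo) as the IV, and pre-treatment assessment score as the covariate". The decision rests on one coefficient: "Confirmation of MT's benefit will be tested in the main effect of therapy type". C.11 names no variance structure, robust standard error, Welch-type test or permutation test.

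The abstract gives a "target enrollment of 100 chronic stroke patients". Under C.7.a, "we will assign patients to the MT and placebo treatment groups in a 2:1 ratio, respectively", which is about 67 and 33. C.7.a accepts the imbalance because "This inequality in sample size will only reduce statistical power by approximately 3"%.

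On variability, B.1 reports that in an earlier MT trial "improvement in the Brunnstrom scale outcome measure ranged from 0% to 33"%, taken as two SDs either side of a mean of 16.5%. Aim 3 rests on the expectation that patients respond differently to MT. On the control, C.7.a says only that an earlier trial with the same placebo "showed little benefit of the placebo therapy".

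The document gives no SD by arm, no residual SD for any outcome, and no alpha, power or effect size for Aim 1.

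**The concern.** Ordinary ANCOVA estimates one residual variance from both arms together. With equal arms, the standard error of the treatment difference is then close to correct even if the variances differ. At 2:1 it is not, because the larger arm dominates the pooled estimate while the smaller arm contributes most to the true variance of the difference.

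If MT adds patient-to-patient variation in response and placebo adds little, the larger arm is also the more variable one. The pooled standard error is then too large. At stake are power and interval width in the test that decides whether home-based MT works.

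**Working it through.** **Inputs.** From the document: N = 100 and 2:1 allocation, so 67 MT and 33 placebo. Assumed: two-sided alpha 0.05, no dropout, 80% power for illustration, and the ratio r = MT residual variance / placebo residual variance.

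**Step 1: the plan's own figure.** With equal variances, the variance of the difference is proportional to 1/50 + 1/50 = 0.040 at 1:1 and to 1/66.7 + 1/33.3 = 0.045 at 2:1. The 2:1 power is Φ[(1.96 + z)·√(0.040/0.045) − 1.96], where z is the normal quantile of the 1:1 power. For 1:1 powers of 80 / 85 / 90 / 95% this gives 75.2 / 80.7 / 86.4 / 92.5%, a loss of 4.8 / 4.4 / 3.7 / 2.5 points. The stated figure of about 3% is reproduced to within 2 points. It presumes equal variances.

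**Step 2: pooled against true standard error.** Set the placebo variance to 1.

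- True variance of the difference: r/67 + 1/33 = (33r + 67)/(67·33).
- Pooled version: [(67r + 33)/100]·(1/67 + 1/33) = (67r + 33)/(67·33).
- Standard-error ratio k = √[(67r + 33)/(33r + 67)].

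For r = 2, k = √(167/133) = 1.12. Rejection rate at zero mean effect = 2[1 − Φ(1.96k)]. Power, where a correct standard error gives 80%, = Φ(2.80 − 1.96k).

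| r | k | Rejection at zero mean effect | Power |
|---|---|---|---|
| 0.5 | 0.89 | 8.0% | 85.4% |
| 1.0 | 1.00 | 5.0% | 80.0% |
| 1.25 | 1.04 | 4.2% | 77.8% |
| 1.5 | 1.07 | 3.6% | 75.9% |
| 2 | 1.12 | 2.8% | 72.8% |

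The higher power at r = 0.5 is not a gain, because the test there exceeds its nominal level.

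**Step 3: simulation of the ANCOVA.** The setting was 67:33 with one baseline covariate and t critical values on 97 degrees of freedom, with 20,000 null runs and 8,000 power runs per ratio.

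| r | Type I error: pooled / HC3 / HC2 | Power: pooled / HC3 / HC2 |
|---|---|---|
| 0.5 | 7.8 / 4.8 / 5.2% | 84.9 / 78.2 / 79.4% |
| 1.0 | 5.1 / 4.8 / 5.3% | 78.6 / 77.5 / 78.7% |
| 1.5 | 3.5 / 4.5 / 4.8% | 74.8 / 78.1 / 79.1% |
| 2 | 2.9 / 4.7 / 5.1% | 71.4 / 77.9 / 78.9% |

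The formula is confirmed, and the robust standard errors hold the level in both directions.

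**The case against.** The strongest case against is that nothing in the document shows r > 1. A weak placebo effect describes a mean. The 0% to 33% range is total spread in one arm of another trial, on a scale that is not an outcome here, and it includes measurement error that placebo patients share. This stands: the size of the problem is unknown, and it is zero at r = 1.

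The same B.1 figure can also be used to bound r. It implies an SD of 33/4 = 8.25, half the mean of 16.5. At 67:33, 80% power corresponds to an effect of 2.80·√(1/67 + 1/33) = 0.60 residual SD. Response SD is then at most 0.30, and r at most 1 + 0.30² = 1.09, if response adds independently to noise and placebo changes little. There k = 1.015 and power is 79.1%. This stands only for a design with 80% power. For an effect of 1 residual SD, the same reasoning allows r = 1 + 0.5² = 1.25. Power is then not the issue, but the interval is still 4% too wide.

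Ratios near 2 also need strong heterogeneity. At r = 2 the SD of individual effects equals the residual SD. With an effect of 2.80·√(2/67 + 1/33) = 0.69, about 25% of patients would be made worse by MT (normal effects assumed). The document suggests nothing of the kind, so r = 2 is the far end of the range.

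A reader might infer three stronger things that the document does not support:

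- **The Aim 1 p-values are wrong.** They are wrong only if the arm variances differ, and that is not established.
- **False positives are inflated.** In the expected direction the test is conservative. If MT affects no patient, the arms share one variance and alpha is nominal. The rates below 5% need a mean effect of zero with some patients helped and others harmed. Inflation needs placebo to be the more variable arm.
- **C.13.a already handles unequal variances, so C.11 is inconsistent with it.** The words "while taking into account the variances within each group" also fit an ordinary pooled t. That comparison is within the MT group only, and inference there is by permutation.

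**Conclusion.** The point holds conditionally. C.11 as written implies a pooled variance, allocation is about 67:33, and any difference in residual variance between arms miscalibrates the standard error. The premise of Aim 3 makes a larger MT variance plausible. For ratios of 1.0 to 2, the cost is a standard error 0 to 12% too large and about 0 to 7 points of power where 80% is expected, most likely towards the lower end. All of these sizes rest on assumed ratios, an assumed two-sided alpha of 0.05 and full follow-up. The mechanism is certain and the magnitude is not. This is a cheap improvement of low to moderate severity, not a flaw that invalidates Aim 1.

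**What to change.** In C.11, keep the same ANCOVA and estimate. State that the test and 95% confidence interval for therapy type will use heteroscedasticity-consistent standard errors (HC2, or HC3) for every primary and secondary outcome at both post-treatment visits, and that the residual SD will be reported by arm. Name the version before unblinding, because the ratio may differ between outcomes and a choice made after seeing the data is open to challenge.

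The change is one sentence, with no new data. If variances are equal, HC2 costs essentially no power. HC3 costs about 1 point at n = 100. For the VRLAT, measured in right-hemisphere patients only, HC3 costs about 2 points (77.5% to 75.2%) if about half the sample qualifies (assumed 33:17). That favours HC2.
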